9.7 Visit 7 (Week 14/ Day 99 \pm 4)

At this visit, the investigator or designee will:

Sponsor Name: Actavis, LLC Protocol: 094-3153-301, v1.0

• Perform the AK lesion count as described in **Section 10.1**. NOTE: New AK lesions need to be identified, counted and recorded. A new AK lesion is one that was not present at the Baseline Visit.

- Perform the LSR assessment as described in **Section 10.2**.
- Query the subject about any changes in health status or any adverse events since the last visit. Document in the AE section of the CRF, as appropriate.
- Collect any used or unused test article pumps and diaries not returned at the previous visit and document on the Test Article Accountability Log as described in **Appendix 2**.
- Record any changes in the subject's concomitant therapies.
- Perform a UPT, if applicable.
- Complete the End of Study Form.

9.8 Unscheduled Visits

The investigator may see the subject at an unscheduled visit to manage any AEs or LSRs. During this visit, the investigator or designee will:

- Query the subject about any changes in health status or any adverse events since the last visit. Document in the AE section of the CRF, as appropriate.
- Perform the LSR assessment as described in **Section 10.2**.
- Record any changes in the subject's concomitant therapies.
- Review subject diary and the requirements for test article application, if applicable.
- Confirm the next visit.

10. CLINICAL EVALUATIONS

The following clinical evaluations will be performed according to the schedules indicated during the study. The same investigator should complete the evaluations for a given subject throughout the study. If this becomes impossible a sub-investigator with overlapping experience with the subject and the study should complete the evaluations.

10.1 AK Lesion Counts

AK lesion counts will be performed at Visit 1, 6 and 7.

he number and location of AK lesions to be treated that are ≥ 4 mm in diameter and the diameter of each AK lesion in the treatment area will also be documented at the Baseline Visit. The suggested procedure for AK counting and definition of full face and balding scalp will be detailed in a separate document. At the Baseline Visit, the treatment area must include at least 5 and no more than 20 clinically typical, visible or palpable AKs, each at least 4 mm in diameter, in an area greater than 25 cm² on either the face (excluding ears) or the balding scalp, but not both. At Visits 6

Sponsor Name: Actavis, LLC Protocol: 094-3153-301, v1.0

and 7, the number of total AK lesions in the treatment area will be counted and the number of new AKs will be identified. A new AK is defined as a lesion that was not present at the Baseline Visit.

If the subject has a LSR that prevents the investigator or designee from performing the AK count at a visit, the investigator or designee should document in the source document and CRF that the AK count was unable to be obtained due to a LSR.

At the Baseline Visit, estimate the surface area of the entire treatment area (full face or balding scalp) to be treated with the test article as a percentage of the total body surface area (BSA). For this assessment, the subject's palmar surface of the hand (palm and fingers/thumb held together) is 1% BSA.

10.2 Local Skin Reactions (LSR) Assessment

At Visit 1, 3, 4, 6, 7 and Unscheduled Visits, if applicable (prior to test article application), the investigator or designee will assess the treatment area and rate on a scale of 0 = none, 1 = mild, 2 = moderate and 3 = severe (through observation and subject query) the following LSRs:

- Erythema
- Edema
- Erosion/ulceration
- Scabbing/crusting
- Weeping/exudate
- Flaking/scaling/dryness
- Pain (within the last 24 hours)
- Pruritus (within the last 24 hours)

These LSRs will be collected independently of adverse events. Any LSR that occurs within the treatment area (full face [excluding the ears] or balding scalp) and extends to adjacent surrounding skin (defined to be up to a 5 cm border around the treatment area) will be considered LSRs. LSRs that require medical intervention (prescription medication) or extend beyond the 5 cm surrounding skin should be documented as an adverse event. LSRs may be of such intensity that the subject may require rest periods (see Section 6.3 for details on rest periods).

11. PHOTOGRAPHY

Photography documentation is not required in this study. The investigator may elect to photograph the subject's treatment area to document the effects of treatment, adverse events or other findings during the trial. All photographs taken as part of this study are for informational purposes only and are not to assist in grading or for any other assessment.

Sponsor Name: Actavis, LLC Protocol: 094-3153-301, v1.0

12. LABORATORY TESTS

12.1 Urine Pregnancy Tests

Urine pregnancy tests must be performed on all WOCBP at baseline prior to randomization and at the EOS visit. All WOCBP must have a negative pregnancy test at baseline to be eligible for study entry. The urine pregnancy testing will be performed at the study site if the site is registered and conforms to CLIA regulations for such testing or at an appropriately registered reference laboratory. The investigator will report the urine pregnancy test results on the case report forms, in the subject's medical records and in independent records maintained at the study site. The urine pregnancy test used must have a minimum sensitivity of 25mIU of $\beta\text{-HCG/mL}$ of urine.

13. END OF STUDY CRITERIA

At the end of each subject's participation in the study, the investigator will complete an End of Study form for all completed and discontinued subjects.

13.1 Completion of the Study

Subjects who complete the two, 2-week cycles of treatment and all of the Visit 7 follow-up evaluations at Week 14 will be considered to have completed the study.

13.2 Subject Discontinuation

A subject may be withdrawn from the study prior to completion for any of the following reasons:

- Adverse event
- Death
- Lack of efficacy
- Lost to follow-up
- Noncompliance with study drug
- Physician decision
- Pregnancy
- Progressive disease
- Protocol violation
- Study terminated by Sponsor
- Withdrawal by subject

If a subject withdraws prematurely for any reason, the site should make every effort to have the subject return for; a) their next scheduled visit to perform all required visit activities and to collect and reconcile all test article AND b) return for the EOS visit (Week 14) to perform all required visit activities and complete the EOS Case Report Forms. If the subject will not agree to return for the EOS visit, the site should complete

Sponsor Name: Actavis, LLC Protocol: 094-3153-301, v1.0

the EOS CRFs during the last visit that the subject will complete. Subjects who withdraw prematurely will not be replaced. When a subject is withdrawn from the study for a treatment-related adverse event, when possible, the subject should be followed until resolution of the adverse event. If a subject is discontinued from the study due to pregnancy, the pregnancy and its outcome should be followed (see **Section 14.4**).

13.3 Study Termination

The study may be terminated by the investigator or the Sponsor. If, in the opinion of the investigator, clinical observations made during the study suggest that it may be unwise to continue, he or she may stop the study. A study termination by the investigator will be reported to the Sponsor.

In addition, a written statement fully documenting the reasons for this action will be submitted to the Sponsor by the investigator within five working days.

In the event that the Sponsor chooses to discontinue or terminate the study, appropriate notification will be given to the investigator.

14. ADVERSE EVENT REPORTING

14.1 Definitions

The following definitions will be utilized:

Adverse Event (AE) - Any untoward medical occurrence associated with the use of a drug in humans, whether or not considered drug related. An AE can therefore be any unfavorable and unintended sign (including an abnormal laboratory finding, for example), symptom, or disease temporally associated with the use of a test article, whether or not considered related to the test article.

Adverse Drug Reaction (ADR) - Any adverse event caused by a drug. Adverse reactions are a subset of all suspected adverse reactions for which there is reason to conclude that the drug caused the event.

Suspected Adverse Reaction (SAR) – Any AE for which there is a reasonable possibility that the drug caused the event. A "reasonable possibility" means that there is evidence to suggest a causal relationship between the drug and the adverse reaction.

Serious Adverse Event (SAE) - Any untoward medical occurrence that at any dose in the view of either the investigator or the Sponsor:

- Results in death
- Is life-threatening (i.e., its occurrence places the patient or subject at immediate risk of death),

Sponsor Name: Actavis, LLC Protocol: 094-3153-301, v1.0

• Requires inpatient hospitalization or prolongation of existing hospitalization with the following exceptions:

- Hospitalization for preplanned treatment for an existing condition
- Hospitalization for social reasons (in countries which permit such hospitalization)
- Hospitalization required for protocol-required-testing or efficacy measurement.
- Results in persistent or significant incapacity or substantial disruption of the ability to conduct normal life functions, or
- Is a congenital anomaly/birth defect
- Important medical event

Important medical events that may not result in death, be life-threatening, or require hospitalization may be considered a serious adverse drug experience when, based upon appropriate medical judgment, they may jeopardize the patient or patient may require medical or surgical intervention to prevent one of the outcomes listed in this definition. Examples of such medical events include allergic bronchospasm requiring intensive treatment in an emergency room or at home, blood dyscrasias or convulsions that do not result in hospitalization, or the development of drug dependency or drug abuse.

Unexpected adverse drug reaction: An AE, whether serious or non-serious, is designated an unexpected (unlabeled) drug related event if it is not consistent with the risk information in the Investigator Brochure, general investigational plan or Package Insert (marketed drugs) or if the event is shown to have a materially greater frequency or severity than previously reported; then such event(s) will be reported to the investigators if, in the opinion of the medical monitor, such findings represent a material drug related event.

Test article: A pharmaceutical form of an active ingredient (or "primary operational component" for devices) or vehicle/placebo being tested or used as a reference in the study, whether blinded or unblinded.

14.2 Reporting of Adverse Events

Throughout the clinical trial the clinical trial staff will question the subject in a non-directive way as to the occurrence of adverse events. All adverse events which were not present at screening must be recorded in the subjects' case report forms, whether observed by the investigator, the investigator's staff, or spontaneously reported by the subjects. If known, the investigator should report the diagnosis of the underlying illness or disorder, rather than its individual symptoms. Follow-up of adverse events will continue through the last day of the study, until the investigator determines outcome, stabilization, and/or resolution of the event, or not-relatedness to study medication, or up to 30 days after the last dose of study drug. For SAEs this can occur before or after day

Sponsor Name: Actavis, LLC Protocol: 094-3153-301, v1.0

30. In the event of death, if an autopsy is performed, a copy of the report should be sent to

The most common AEs reported with the use of imiquimod cream, 2.5% include LSRs listed by decreasing frequency: erythema, scabbing/crusting, flaking/scaling/dryness, edema, erosion/ulceration and weeping/exudate. Other application site reactions that have been reported include pruritus, irritation, pain, bleeding and swelling. LSRs may range in severity from mild to severe and may extend beyond the treatment area to the surrounding skin. LSRs occurring within the treatment area will be assessed at each visit and documented as detailed in **Section 10.2**. Any LSR that requires medical intervention (prescription medication) or extends beyond the 5 cm surrounding skin should be documented as an adverse event. Other reported AEs occurring in \geq 2% of imiquimod cream, 2.5% treated subjects are listed in the Package Insert for Zyclara.

14.2.1 Adverse Event and SAE Reporting Period

The AE and SAE reporting period starts following the subject's written consent to participate in the clinical trial with the first trial related procedure and ends after the last treatment dose.

Adverse events classified as "serious" require expeditious handling and reporting to TI to comply with regulatory requirements. All SAEs whether related or unrelated to test article must be immediately reported to TI by email, telephone or confirmed facsimile transmission to the Medical Monitor or Project Manager listed on the first page of the protocol. Follow-up of AEs and SAEs is to occur as described in **Section 14.2**.

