- 4. Visit 4 (Day 29 ± 2): Subjects will return for LSR and AE assessment. Concomitant medications will be reviewed. The subject diary card for treatment cycle 2 will be dispensed. Test article for treatment cycle 2 will be dispensed. Any uncollected test article from treatment cycle 1 will be collected. Subjects will be scheduled for the next visit. NOTE: Visit 6 should be scheduled 14 to 17 days after Visit 4.
- 5. Visit 5 Phone Call (Day 36 ± 2): The site staff will contact the subject on Day 36 to confirm the next visit appointment, review application instructions and query about AEs. Remind the subject to continue to apply up to two (2) pump actuations of test article once daily in the evening and to stop after the subject has treated for 14 consecutive days after Visit 4, even if Visit 6 is scheduled after 14 consecutive application days have elapsed.
- 6. Visit 6 (14-17 Days after Visit 4): Subjects will return for an AK lesion count, LSR and AE assessment. Compliance with test article application and concomitant medications will be reviewed. The subject diary card and test article will be reviewed and collected. Subjects will be scheduled for the next visit.
- 7. Visit 7 (Day 99 ± 4): Subjects will return for the final AK lesion count, LSR and AE assessment. Concomitant medications will be reviewed. A UPT, if applicable, will be obtained. Any uncollected test article or diaries will be collected.

Study Measurements

Efficacy

The primary efficacy parameter is the number of all visible or palpable AK(s) (baseline and new lesions) in the treatment area as enumerated at Visits 1, 6 and 7 by the investigator.

Safety:

All AEs will be recorded. At each visit, subjects will also be questioned

Sponsor Name: Actavis, LLC Protocol: 094-3153-301, v1.0

	specifically about any AEs associated with the application of the test article as well as the status of any AEs. In addition, LSRs including erythema, edema, weeping/exudate, flaking/scaling/dryness, scabbing/crusting, erosion/ulceration, pain and pruritus) will be assessed separately at each visit by the investigator as detailed in Section 10.2 .

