6.2.3 Adverse Events

An adverse event (AE) is defined as any untoward medical occurrence associated with the use of a drug in humans, whether or not considered drug related. An AE can therefore be any unfavorable and unintended sign (including an abnormal laboratory finding, for example), symptom, or disease temporally associated with the use of a test article, whether or not considered related to the test article.

Any AE caused by a drug is an adverse drug reaction (ADR). ADRs are a subset of all suspected adverse reactions for which there is reason to conclude that the drug caused the event. Any AE for which there is a reasonable possibility that the drug caused the event is a suspected adverse reaction (SAR). Serious adverse events (SAE) are defined as any untoward medical occurrence that at any dose in the view of either the Investigator or Sponsor results in death, is life-threatening, requires inpatient hospitalization or prolongation of existing hospitalization, results in persistent or significant incapacity or substantial disruption of the ability to conduct normal life functions, or is a congenital anomaly/birth defect.

The AE and SAE reporting period starts following the subject's written consent to participate in the clinical trial with the first trial related procedure and ends after the last treatment dose. Throughout the clinical trial the subject will be questioned in a non-directive way as to the occurrence of adverse events. All adverse events which were not present at Screening will be recorded. Adverse events will be followed through the last day of the study, until the investigator determines outcome, stabilization, and/or resolution of the event, or not-relatedness to study medication, or up to 30 days after the last dose of study drug.

[figure not shown]
The severity of an AE will be recorded as mild, moderate or severe. The relationship between an AE and the test article will be classified as certain, probable, possible or not related. The AE outcome will be specified as not recovered/resolved, recovered/resolved, recovered/resolved with sequelae, recovering/resolving, fatal, or unknown.

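### The AE/SAE reporting period is stated to end after the last dose (nominal Day 42), yet AEs are collected at Visit 7 (Day 99)

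*Protocol*

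**What the plan says.** **The reporting period.** Protocol 14.2.1 is the section that defines it. The period starts after written consent, "with the first trial related procedure and ends after the last treatment dose". SAP 6.2.3 uses the same words. The same protocol section also states: "All SAEs whether related or unrelated to test article must be immediately reported".

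**Collection of AEs.** For Visit 7 (Day 99 ± 4) the synopsis says: "Subjects will return for the final AK lesion count, LSR and AE assessment". The AE row is marked at all seven contacts in both the protocol and SAP schedules, and SAP 5.2 lists AEs among the Visit 7 procedures. Protocol 9.7 instructs the site at Visit 7: "Query the subject about any changes in health status or any adverse events since the last visit", with entry in the AE section of the CRF. Protocol 14.2 has staff question subjects for the whole of the trial and says "All adverse events which were not present at screening must be recorded". SAP 6.2.3 places a similar sentence, "All adverse events which were not present at Screening will be recorded", in the same paragraph as the end-of-dosing limit.

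**Local skin reactions (LSRs).** Protocol 10.2 scores them at Visit 7, among other visits, and adds: "LSRs that require medical intervention (prescription medication) or extend beyond the 5 cm surrounding skin should be documented as an adverse event".

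**Follow-up of known events.** Protocol 14.2 and SAP 6.2.3 give several alternatives, including the last day of the study "or up to 30 days after the last dose of study drug", and do not say which governs. Protocol 14.2 relaxes the 30-day limit for SAEs.

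**Tables.** The protocol synopsis and 17.3.2.2 summarise treatment-emergent AEs. SAP 8.8.1 tabulates AEs, and applies Fisher's exact tests to those at 2% or more, without that restriction. The visible text of neither document defines the term.

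**The concern.** Safety is part of the stated objective. A site that takes 14.2.1 literally would not report an AE that begins after the last application. A site that follows the schedule and 9.7 would. With about 25 sites, capture after dosing could depend on which page a coordinator reads.

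The second mismatch is smaller. Because the reporting period opens before the first dose, SAP 8.8.1 as written can count pre-dose events that the protocol's table would leave out.

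**Working it through.** **Inputs**
- Visit 4, when cycle 2 test article is dispensed: Day 29 ± 2, i.e. Day 27 to 31 (schedules of events).
- Each cycle: 14 consecutive days, not extended for missed or held doses (protocol 6.2, 6.3).
- Day count: cycle 1 ends with the Day 14 application (protocol 9.2), so the last dose is the starting day + 13. Assumption: cycle 2 starts on the evening of Visit 4, as cycle 1 does at Visit 1.
- Visit 6: 14 to 17 days after Visit 4.
- Visit 7: Day 99 ± 4, i.e. Day 95 to 103.

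**Reproducing the plan's own figure.** Last dose = 29 + 13 = Day 42. The first day off treatment is Day 43, and 43 + 56 = Day 99. Also 1 + 14 × 7 = Day 99. The plan's end-of-study visit 8 weeks after treatment therefore agrees with a nominal last dose on Day 42.

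**Time between the stated end of reporting and Visit 7**

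| Quantity | Nominal | Across windows |
|---|---|---|
| Last dose (Visit 4 + 13) | 29 + 13 = Day 42 | 27 + 13 = 40 to 31 + 13 = 44 |
| Last dose to Visit 7 | 99 − 42 = 57 days | 95 − 44 = 51 to 103 − 40 = 63 |
| Last dose to Visit 6 | – | 14 − 13 = 1 to 17 − 13 = 4 days |
| Stopped after cycle 1 (Day 14), returns at Week 14 | 99 − 14 = 85 days | 95 − 14 = 81 to 103 − 14 = 89 |

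The 57 days are 57/98 = 58% of the span from Day 1 to Day 99. Two of the seven scheduled contacts, Visits 6 and 7, come after the last dose. The 85-day row applies because protocol 13.2 asks early withdrawals to return at Week 14.

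If cycle 2 began the day after Visit 4, the last dose would be Day 43 (41 to 45) and the gap 99 − 43 = 56 days (95 − 45 = 50 to 103 − 41 = 62). The conflict is unchanged.

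**The follow-up limit, a separate rule.** Thirty days after the last dose is 42 + 30 = Day 72 (70 to 74). That is 99 − 72 = 27 days before Visit 7 (95 − 74 = 21 to 103 − 70 = 33). The two named calendar limits for follow-up therefore differ by about four weeks. This limit governs how long a known event is followed and does not extend the reporting period.

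**Can the texts be read together?**
- *Visits 6 and 7 only follow up earlier events.* This fails: 9.6 and 9.7 ask for any events since the previous visit and send them to the CRF.
- *The phrase in 14.2.1 is loose and fixes no day.* Then the only section that defines the period gives no usable end.
- *SAEs.* Here other text favours reporting: 14.2.1 itself calls for all SAEs, related or not; 14.2.3.1 sets no onset limit on the 24-hour form; and 14.2.4 sends all SAEs to the IRB. Section 14.2.3.1 adds that SAEs after the *study period* are reported if possibly related. The visible text does not define that term, but it can be read as running to Visit 7, where 13.1 places study completion.

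**Pre-dose events.** Reporting starts with the first trial procedure after consent, which may be up to 30 days before Visit 1. The number of pre-dose AEs cannot be estimated from the documents.

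**The case against.** The best defence is that one general sentence stands against explicit instructions at every visit. A site would have to disregard 9.6, 9.7, 14.2 and the schedule to lose an event. No analysis section limits the tables to the 14.2.1 period, LSR scores and new AKs are recorded separately at Visits 6 and 7, and SAEs are called for elsewhere. On this view the phrase names no calendar day, so a 57-day gap is read into it, and the Day 72 figure belongs to a different rule.

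Much of this stands. The documents do not show that events would be lost, the 57 days assume that the period closes on the day of the last dose, and the follow-up limit is a separate rule. The conflict itself remains: the section a site consults to learn when reporting stops gives an answer that the visit instructions contradict, and the SAP repeats it.

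On treatment-emergent AEs, the AE definition in both documents ties an AE to use of the test article, which could be read as already excluding pre-dose events. Where no washout is needed, screening and baseline can fall on one day, so exposure may be nil. That makes the point minor. It does not remove it, because the reporting period explicitly starts before dosing and the two documents describe the tables differently.

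**Conclusion.** The inconsistency is real and should be corrected. Protocol 14.2.1 and SAP 6.2.3 end AE/SAE reporting after the last dose, while the synopsis, both schedules, SAP 5.2 and protocol 9.7 require AE collection at Visit 7. On the assumption that cycle 2 starts on the evening of Visit 4 and that the period closes with the last dose, 57 days (51 to 63) lie between the two end points, or 85 days (81 to 89) for a subject who stops after cycle 1 and returns at Week 14. The finding is a conflicting rule, not a plain stop to collection, and it mainly concerns non-serious AEs with onset after dosing.

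The missing treatment-emergent restriction in SAP 8.8.1 is a separate, minor mismatch. It would add noise rather than bias to the AE tables and Fisher tests, and the Safety population already excludes subjects who never received test article. Equivalence and superiority rest on complete clearance and are not touched by either point.

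**What to change.** 1. Reconcile protocol 14.2.1 and SAP 6.2.3 with the schedules of events and 9.7, so that a single AE/SAE reporting end point applies. The schedules already collect AEs at Visit 7.
2. Make the follow-up limit in 14.2 and SAP 6.2.3 consistent with that end point and say which alternative governs. Define *study period* in 14.2.3.1 to match.
3. In SAP 8.8.1, restrict the tables and Fisher tests to treatment-emergent AEs, as protocol 17.3.2.2 does. Define the term once, for example as onset on or after the first application, and say how a pre-dose event that worsens on treatment is counted. List pre-dose events separately.

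The cost is rewording of protocol 14.2, 14.2.1 and 14.2.3.1 and of SAP 6.2.3 and 8.8.1. No visit or procedure is added, because AEs are already queried at Visits 6 and 7. The downside is slightly more SAE paperwork during follow-up.
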